4.2.20 History of seizures

4.3 Restrictions

Because of the teratogenic nature of VPA, female patients must be six months postmenopausal, surgically sterile, or using an acceptable method of contraception. Female patients must agree to continue using an acceptable method of contraception for a period of three months after study medication administration. Acceptable methods of contraception are oral contraceptives, barrier methods, approved contraceptive implant, long-term injectable contraception, intrauterine device or tubal ligation.

5.0 Treatment Plan

5.0 Treatment Plan

Chronic dosing has been suggested to be more effective for targeted therapies in pre-clincial studies. As such a dosing regimen found to be relatively non-toxic has been selected for chronic administration with concurrent standard agents (details above). Patients will initially receive daily oral VPA 15 mg/kg/day divided in three doses or placebo divided into three doses. Based on the patient's bmi, obese patient dosing will be based on the adjusted body weight calculated using the MD Anderson Clinical Calculator Formula (<http://inside2.mdanderson.org/apps/calculators/calc1.cfm>). Body mass index is a measure of body fat based on height and weight (applies to both men and women adults)

BMI	Weight Status
-----	---------------

Below 18.5	Underweight
18.5 – 24.9	Normal
25.0 – 29.9	Overweight
30.0 and Above	Obese

If the patient tolerates the reduced dose for 10 consecutive days then the VPA dose will increase to 30 mg/kg/day divided into three doses or placebo divided into three doses. The patient will be contacted by phone to assess tolerance and instruction to increase dose. Daily dose in mg will be divided by 250 mg and rounded down to a whole number of capsules to determine the number of VPA tablets or placebo tablets to be taken 3 times per day. Depending on the time of indwelling pleural catheter placement, on day 1 of treatment the patient may take 1, 2, or 3 doses. The research team will instruct the patient on the number of doses to take on day 1. Patients will be instructed to take the VPA at approximately the same time each day. Patients will be instructed to take the pills with food. Study drug compliance will be verified by a returned pill diary. Patients will be treated for 10 weeks. We anticipate this study will be activated in January 2014 and will be completed in January 2016.

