3.4 On-Study Evaluations

On the day of indwelling intrapleural catheter placement the patient's pleural fluid will be drained, recorded and sent for cytology review. On the day of indwelling intrapleural catheter placement patients will receive VPA or **placebo** if cytology is positive. Patients will be provided a diary to record drainage from home.

Patients will be treated for the whole period of 10 weeks, and clinical course of disease will be monitored throughout this time. (Note: evaluations may be done within \pm 7 business days of the date specified in the protocol).

Patients will initially receive daily oral VPA 15 mg/kg/day divided in three doses or placebo divided in three doses. Based on the patient's bmi, obese patient dosing will be based on the adjusted body weight calculated using the MD Anderson Clinical

Calculator Formula (<http://inside2.mdanderson.org/apps/calculators/calc1.cfm>). If the patient tolerates the reduced dose for 10 consecutive days then the VPA dose will increase to 30 mg/kg/day divided into three doses or placebo divided into three doses. The patient will be contacted by phone to assess tolerance and instruction to increase dose. Daily dose in mg will be divided by 250 mg and rounded down to a whole number of capsules to determine the number of VPA tablets or placebo tablets to be taken 3 times per day.

Evaluations may occur any time during weeks 2, 6, and 10.

- 3.4.1 Patients will document daily amount of pleural fluid drainage.
- 3.4.2 Patients will be evaluated at weeks 2, 6, and 10 with complete interim histories and physical examinations including measurement of vital signs, performance status, weight and medical history.
- 3.4.3 Patients will complete a EQ-5D and St. George's respiratory questionnaire, at weeks 2, 6, and 10 in person, via telephone or electronic media.
- 3.4.4 Blood samples for CBC with differential, platelet count, and PT/PTT/INR, serum and plasma banking, and optional CTC (if patient agrees) assessment will be collected prior to treatment and at weeks 2, 6 and 10.
- 3.4.5 Tests to measure serum electrolytes, BUN, creatinine, glucose, albumin, alkaline phosphatase, AST or ALT, LDH, total bilirubin, amylase, lipase, magnesium and ionized calcium will be performed at weeks 2, 6, and 10.
- 3.4.6 Optional urine (if patient agrees) will be collected prior to treatment and at weeks 2, 6 and 10.
- 3.4.7 Chest x-ray will be performed immediately after catheter placement and at weeks 2, 6, and 10.

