5.2 Dose Modification Summary

Attributions will be made using clinical judgment and assigned as definite probably possible etc...as per the human subjects research manual Chapter 15.001 (inside MDA).

Valproic acid serum levels will be drawn where indicated and for grade II toxicity not possibly related to other systemic treatments. Results will be reviewed by the study research nurse. Abnormally high values (increased above upper limit normal) will be reported to the treating physician, will be considered in the clinical attribution, and the patient will become unblinded and IND monitor notified. Subsequent serum monitoring will be at the discretion of the treating physician.

2. Attribution changes to above category based on best judgement with ongoing clinical evaluation and data.

[figure not shown]
Table 1 - Starting Dose Reduction Example

Dose	Toxicity (see 5.2 and 5.3)	Dose reduced by 5mg/kg/day	Calculation Example	Number of capsules
Starting dose	Dispense 250 mg capsule e.g. (70 kg pt) per day	Reduced dose	Dispense 250 mg capsule per day	Number of capsules to be taken approx. every 8 hours
15 mg/kg/day	Dispense 4 capsules 15mg/70kg/day $15 \times 70 = 1050$ Rounded down to 1000 mg = 4 capsules	10 mg/kg/day	Dispense 2 capsules 10mg/70kg/day $10 \times 70 = 700$ Rounded down to 500 mg = 2 capsules	Take one capsule every 12 hours (if this scenario were to occur this is not a protocol violation as this is an appropriate dose for such a patient)
10 mg/kg/day	Dispense 2 capsules 5 mg/70kg/day $10 \times 70 = 700$ 700 mg = 2 capsules	5 mg/kg/day	Dispense 1 capsule 5mg/70kg/day $5 \times 70 = 350$ Rounded down to 250 mg = 1 capsule	Take one capsule once a day (if this scenario were to occur this is not a protocol violation as this is an appropriate dose for such a patient)

Table 2 - Dose Reduction Example Full Dose

Dose	Toxicity (see 5.2 and 5.3)	Dose Reduced 10mg/day	Calculation Example	Number of Capsules
Original Dose	Dispensed 250 mg capsules (ie 70 Kg pt) per day	Reduced dose	Dispensed 250 mg capsules per day	Number of capsules to be taken approx. every 8 hours
30 mg/kg/day	8 (30 x 70 = 2100, rounded down to 2000mg = 8 capsules)	20mg/kg/day	5 (20 x 70 = 1400, rounded down to 1250 = 5 capsules)	Dose 1 = 2 capsules Dose 2 = 2 capsules Dose 3 = 1 capsule
20mg/kg/day	5 (20 x 70 = 1400, rounded down to 1250 = 5 capsules)	10mg/kg/day	2 (10 x 70 = 700, rounded down to 500 = 2 capsules)	Dose 1 = 1 capsule Dose 2 = 1 capsule Dose 3 = 0 capsules

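### The round-down capsule rule and the dose-reduction tables do not agree: they give zero capsules at the 5 mg/kg/day level below 50 kg, a unit slip in Table 2, and a threefold conflict over the daily count

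*Combined protocol and SAP*

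**What the plan says.** Section 3.4 sets the start: "Patients will initially receive daily oral VPA 15 mg/kg/day divided in three doses or placebo divided in three doses". Section 5.0 repeats this almost word for word. If the starting dose is tolerated for ten consecutive days, "then the VPA dose will increase to 30 mg/kg/day divided into three doses".

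Both sections convert the dose to capsules by the same rule: "Daily dose in mg will be divided by 250 mg and rounded down to a whole number of capsules". The sentence then makes the result the number of units to be taken on each of three occasions a day.

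Section 5.2 works the rule for one patient of 70 kg. Table 1 (starting-dose ladder) goes from 15 to 10 to 5 mg/kg/day:

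- 15 mg/kg/day: "Rounded down to 1000 mg = 4 capsules"
- 10 mg/kg/day: "Rounded down to 500 mg = 2 capsules"
- 5 mg/kg/day: "Rounded down to 250 mg = 1 capsule"

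Table 1 notes that two capsules a day, or one, is acceptable and not a violation. Table 2 (full-dose ladder) goes from 30 to 20 to 10 mg/kg/day, with 8, 5 and 2 capsules a day, under a column headed "Dose Reduced 10mg/day".

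The eligibility criteria (section 4.0) set no minimum weight, and the BMI table in section 5.0 includes an underweight band.

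**The concern.** A ladder of nominal mg/kg levels combined with a 250 mg capsule and rounding down works only if each level still yields a sensible count at every weight that can be enrolled. The protocol shows this for 70 kg alone. At lower weights the bottom level of Table 1 may yield nothing, and neighbouring levels may deliver amounts far from their labels.

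Two wording conflicts add to this. The rule read literally and the tables differ on whether the rounded number is a daily total or a count per intake, and Table 2's heading and rows use different units.

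At stake are consistent dispensing and the meaning of a recorded dose level. If the label does not identify the amount given, adverse events cannot be related reliably to dose, and the stated exposure of 15 then 30 mg/kg/day cannot be taken at face value.

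**Working it through.** **Inputs.** 250 mg capsule and rounding down (sections 3.4 and 5.0); levels 15, 10 and 5 mg/kg/day (Table 1) and 30, 20 and 10 mg/kg/day (Table 2). Weights other than 70 kg are assumed, because the documents give no weight data.

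**Formulas.** Capsules per day = floor(level x weight / 250). Delivered mg/kg/day = 250 x capsules / weight.

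**Reproducing the tables at 70 kg.**

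| Level (mg/kg/day) | mg/day | mg / 250 | Capsules/day | Delivered mg/kg/day |
|---|---|---|---|---|
| 30 | 2100 | 8.4 | 8 | 28.6 |
| 20 | 1400 | 5.6 | 5 | 17.9 |
| 15 | 1050 | 4.2 | 4 | 14.3 |
| 10 | 700 | 2.8 | 2 | 7.1 |
| 5 | 350 | 1.4 | 1 | 3.6 |

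All five counts match section 5.2, so the tables use a daily total.

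**(a) Zero count.** At 5 mg/kg/day the count is floor(5 x weight / 250). It is 0 whenever 5 x weight < 250, that is, for every dosing weight under 50 kg.

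**(b) Label against delivery.** Capsules per day, with delivered mg/kg/day in brackets:

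| Dosing weight | Labelled 15 | Labelled 10 | Labelled 5 |
|---|---|---|---|
| 35 kg | 2 (14.3) | 1 (7.1) | 0 |
| 40 kg | 2 (12.5) | 1 (6.3) | 0 |
| 45 kg | 2 (11.1) | 1 (5.6) | 0 |
| 49 kg | 2 (10.2) | 1 (5.1) | 0 |
| 50 kg | 3 (15.0) | 2 (10.0) | 1 (5.0) |
| 66.6 kg | 3 (11.3) | 2 (7.5) | 1 (3.8) |
| 70 kg | 4 (14.3) | 2 (7.1) | 1 (3.6) |

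At 49.9 kg the start delivers 500 / 49.9 = 10.0. In the protocol's own 70 kg example, the step labelled 15 to 10 is 5/15 = 33% on the label but (4 - 2)/4 = 50% in capsules.

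**(c) Table 2 unit.** The rows drop by 10 mg/kg/day, which is 700 mg/day at 70 kg. The heading says 10 mg/day. Taken literally, 2100 - 10 = 2090 mg, and 2090 / 250 = 8.36, still 8 capsules.

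**(d) Daily total or per intake.** Read literally, sections 3.4 and 5.0 have the rounded daily count taken three times a day. At 70 kg on the starting dose that is 4 x 3 = 12 capsules, or 3000 mg, against 4 capsules, or 1000 mg, in Table 1: a factor of three. Rounding each intake separately does not match either: 1050 / 3 = 350 mg gives 1 capsule per intake, so 3 a day rather than 4.

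**The case against.** The strongest reply is that the problem is narrow and partly foreseen. Several parts of it stand.

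- *Reach of the zero count.* The 5 mg/kg/day level exists only in Table 1. Reaching it takes a dosing weight under 50 kg and two reductions on the starting-dose ladder. Table 2 bottoms out at 10 mg/kg/day, which yields at least one capsule from 25 kg upward (10 x 25 = 250). The number of patients affected is unknown.
- *Missing figures.* The adverse-event flowcharts are not shown in the text available. They may say what happens when no capsule can be given, so one can say only that the visible text has no such provision.
- *Examples and accepted rounding.* Both tables are labelled as examples, and Table 1 accepts departures from three-times-daily dosing at two capsules or one. That answers a complaint about uneven splitting there. It does not reach a count of zero.
- *Table 2 heading.* The rows make the intended step plain, so a reader would be wrong to infer that no reduction takes place. It remains an error in a dosing table.

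Three stronger inferences are tempting but unsupported. One is that everyone under 50 kg starts near 10 mg/kg/day; the start delivers 12.5 at 40 kg and 14.3 at 35 kg. Another is that the stopping rule is distorted; section 6.0 monitors toxicity leading to dose reduction, and a patient at the 5 level has already been counted at the 15-to-10 step. The third is that a patient with zero capsules would be counted as still on treatment; no section says how such a patient is classified.

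The objection does not remove the threefold conflict between the rule's wording and Table 1, or the gap between label and delivery at ordinary weights such as 66.6 and 70 kg.

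**Conclusion.** The point holds as a failure of sections 3.4, 5.0 and 5.2 to agree. On the daily-total reading, which reproduces all five 70 kg counts:

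- the 5 mg/kg/day level is 0 capsules for every dosing weight under 50 kg;
- the 15 mg/kg/day start delivers 11.1 to 10.0 mg/kg/day from 45 kg to just under 50 kg;
- a labelled 33% reduction is 50% at 70 kg.

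On the literal wording, the daily amount at 70 kg is three times that of Table 1. Table 2's heading contradicts its rows whichever reading is used.

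This rests on the rule as printed, on the absence of a minimum weight in section 4.0, and on assumed weights below 50 kg. It is subject to what the unseen flowcharts say about a zero count. The toxicity stopping count does not change, and no analysis in section 6.0 uses dose level or mg/kg exposure. The loss is in correct dispensing and in interpreting dose level and exposure. Which reading or level is clinically right is not for this review to say.

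**What to change.** Reconcile the capsule rule in sections 3.4 and 5.0 with Tables 1 and 2 in section 5.2:

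1. State whether the rounded number is a daily total or a count per intake.
2. Replace the single 70 kg example with a table giving capsules per day and per intake for each labelled level across eligible dosing weights.
3. State what applies where rounding gives zero, or point to the flowchart that already says so.
4. Correct the unit in the Table 2 heading so that it agrees with the rows.
5. Report delivered mg/day beside the labelled level. The dispensing records (section 5.1.1), the pill diary (section 5.0) and the weights taken at visits (section 3.4) should already supply what is needed.

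The clinical team decides the rounding convention, the levels and the handling of a zero count. The cost is a wording and table amendment and a pharmacy dispensing sheet, with no added patients or visits.

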The second issue to be discussed from the two trials is that, although limited, **preclinical evidence does suggest that like most "targeted therapies", the chronic administration of VPA is required to achieve the best results(42, 43)**. This may have implications regarding the maximum tolerated dose, being possible that short-term administrations of VPA (three or five days) could allow to administer higher doses but for chronic administrations doses such as those encountered safe in the first study would be more suitable, particularly in combination therapies with other cytotoxic or cytostatic drugs. **In summary, it seems that doses between 20 and 60 mg/kg of VPA can be appropriate for further testing in solid tumors as H3 and H4 hyperacetylation in tumors is achievable in most patients.**

Phase I-II studies

A third study with VPA combined with epirubicin was recently published. This was a phase I-II study in patients with advanced solid tumor malignancies, an ECOG performance status of 0-2, and adequate organ function. Prior anthracyclines were permitted (doxorubicin ≤ 300 mg/m² and epirubicin ≤ 600 mg/m²). In this study an intravenous loading dose of VPA was followed by five oral doses administered every 12 h beginning 1 h after the loading dose, though later in the study, the intravenous loading dose was replaced with an oral loading dose. Dose escalation started on 15 mg/kg up to 160 mg/kg. On day 3, 4 h after the last dose of VPA, epirubicin was administered by intravenous infusion in cycles of 21 days. The trial allowed for maximal cumulative doses of 750 mg/m² for epirubicin (or epirubicin equivalent) or the use of a cardioprotectant in patients with clearly documented benefits beyond this dose.

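### Sections 3.4 and 5.0 call the daily capsule total the number to take three times a day; read literally, a 70 kg patient at full dose takes 24 capsules a day instead of 8

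*Combined protocol and SAP*

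**What the plan says.** Section 5.0 starts patients at 15 mg/kg/day in three doses. If this is tolerated for 10 consecutive days, "then the VPA dose will increase to 30 mg/kg/day divided into three doses". Section 3.4 has the same schedule. Both sections then give one rule for converting the dose to capsules: "Daily dose in mg will be divided by 250 mg and rounded down to a whole number of capsules", and the result is used "to determine the number of VPA tablets or placebo tablets to be taken 3 times per day".

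Section 5.2 works the conversion for a 70 kg patient, with column headings that count 250 mg capsules per day:

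- Table 1, 15 mg/kg/day: "Rounded down to 1000 mg = 4 capsules".
- Table 2, 30 mg/kg/day: "8 (30 x 70 = 2100, rounded down to 2000mg = 8 capsules".
- Table 2, reduction to 20 mg/kg/day, 5 capsules in the day: "Dose 1 = 2 capsules Dose 2 = 2 capsules Dose 3 = 1 capsule".

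The tables show how capsules are spread over the day for reduced doses only, not for the two planned doses.

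**The concern.** The rule starts from the daily dose, so its quotient is already a daily count. Calling it the number to be taken three times a day multiplies the dose by three. The tables treat the same quotient as the day's total.

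This is the instruction that staff turn into capsules per administration. They need it on day 1, when Section 5.0 allows one, two or three doses, and again at the telephone call that raises the dose. Valproic acid carries boxed warnings for hepatotoxicity and pancreatitis (Sections 1.2.2 and 5.1.4), and the trial gives it daily for 10 weeks. The review transcribed in Section 1.2.1 concludes that "doses between 20 and 60 mg/kg of VPA can be appropriate for further testing in solid tumors", and it favours the doses of the first phase I study (20 to 40 mg/kg) for chronic use. In the second phase I study, with intravenous dosing on five-day courses, the maximum tolerated dose was 60 mg/kg. Dosing errors would also feed the Section 6.0 rule that can stop the study for toxicity leading to dose reduction.

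**Working it through.** **Inputs.** Capsule strength 250 mg, starting dose 15 mg/kg/day and full dose 30 mg/kg/day (Sections 3.4, 5.0 and 5.2). Weight 70 kg (the example in Tables 1 and 2).

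**Step 1: reproduce the tables.** Capsules per day = floor(dose × weight / 250).

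| Dose (mg/kg/day) | Daily mg at 70 kg | ÷ 250 | Rounded down | Table count |
|---|---|---|---|---|
| 30 | 2100 | 8.4 | 8 | 8 |
| 20 | 1400 | 5.6 | 5 | 5 |
| 15 | 1050 | 4.2 | 4 | 4 |
| 10 | 700 | 2.8 | 2 | 2 |
| 5 | 350 | 1.4 | 1 | 1 |

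Every worked count reproduces as a daily total. The 20 mg/kg/day split confirms it: 2 + 2 + 1 = 5.

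**Step 2: apply the sentence literally.** Capsules per day = 3 × floor(dose × weight / 250).

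- Full dose: 3 × 8 = 24 capsules; 24 × 250 = 6000 mg; 6000 / 70 = 85.7 mg/kg/day. Table 2 gives 2000 mg, or 2000 / 70 = 28.6 mg/kg/day. The ratio to the tabulated dose is 6000 / 2000 = 3.0, and to the nominal dose 85.7 / 30 = 2.86.
- Starting dose: 3 × 4 = 12 capsules; 12 × 250 = 3000 mg; 3000 / 70 = 42.9 mg/kg/day. Table 1 gives 1000 mg, or 14.3 mg/kg/day.

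**Step 3: other weights.** The documents give no weight distribution, so I assume whole-kg dosing weights from 50 to 100 kg (51 values).

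- Literal full dose: lowest at 58 kg, floor(1740 / 250) = 6 and 6 × 750 / 58 = 77.6 mg/kg/day; highest at 50, 75 and 100 kg, 90.0 mg/kg/day. That is 2.59 to 3.0 times nominal and above 60 mg/kg at every weight.
- Literal starting dose: lowest at 66 kg, floor(990 / 250) = 3 and 3 × 750 / 66 = 34.1 mg/kg/day; highest at 50 and 100 kg, 45.0 mg/kg/day. That is 2.27 to 3.0 times nominal and inside the 20 to 60 mg/kg range.

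**Step 4: does the daily total split evenly?** At full dose the total runs from 6 to 12 capsules over these weights. It is 7, 8, 10 or 11 at 8 weights each, so 32 of the 51 weights give a total that does not divide by three. Neither planned total at 70 kg (4 or 8) does.

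**Step 5: a repair that would not work.** Rounding each single dose down gives, at 70 kg, 3 × floor(2100 / 750) = 6 capsules (1500 mg, 21.4 mg/kg/day) at full dose and 3 × floor(1050 / 750) = 3 capsules (750 mg, 10.7 mg/kg/day) at the start. Both disagree with the tables.

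**The case against.** The best answer is that nobody would be misled. The same paragraphs give a mg/kg/day dose divided into three, the rationale in Section 1.3 repeats it for the 30 mg/kg/day dose, and Table 2 works the 70 kg case to 8 capsules per day. The phrase can also be read loosely as a total taken over three administrations. Dispensing records, the pill diary, the research team's day 1 instructions and the escalation call are all safeguards, and serum valproate is drawn for grade 2 or higher events. The capsule arithmetic itself is right, so this is a conflict of wording.

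Much of that stands. The intended dose is not in doubt, the fault is one sentence copied into two sections, and the literal starting dose stays within the range that the background supports. But the loose reading is the less natural one, and clear intent elsewhere does not correct an instruction printed twice. The returned diary and the serum levels act only after a dose has been taken.

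On the missing split, the tables are examples of dose reduction and show by example how an uneven total is handled. A figure that cannot be read here may show the split for the planned doses, so I do not claim that the plan lacks it. Such a figure would not remove the conflict between the sentence and the tables.

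**Conclusion.** Wrong as written, and it should be corrected. The sentence in Sections 3.4 and 5.0 contradicts Tables 1 and 2. At 70 kg, following it gives three times the tabulated dose: 24 capsules against 8 at full dose, and 12 against 4 at the start. For assumed weights of 50 to 100 kg, the literal full dose is 77.6 to 90 mg/kg/day, always above the 20 to 60 mg/kg that the background supports. I do not suggest that the plan intends this dose or that an overdose is likely. The case for acting is that this is a safety-relevant dosing instruction and the repair costs almost nothing. The 70 kg figures rest only on numbers in the protocol; the ranges and the 32-of-51 count rest on the assumed weights.

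**What to change.** - In Sections 3.4 and 5.0, state that the daily dose in mg divided by 250 and rounded down is the **total number of capsules per day**, split as evenly as possible over three doses.
- Add the split for the two planned doses to Tables 1 and 2. At 70 kg this is 2 + 1 + 1 for 4 capsules and 3 + 3 + 2 for 8. Have pharmacy confirm the wording.
- Do not repair the sentence by rounding each single dose down, which would underdose relative to the tables.
- In the same amendment, correct the Table 2 heading "Dose Reduced 10mg/day" to 10 mg/kg/day. Its rows step from 30 to 20 to 10 mg/kg/day, so this is a slip of units only.

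The cost is one sentence in each of two sections, one added split per table and one heading. The intended dose, sample size and analysis are unchanged.
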